### Study Title

Peri-Operative Neutrophil:Lymphocyte Ratio (NLR) as a Predictor of Outcomes Following Emergency General Surgery During the COVID-19 Pandemic

### Study Design

Observational study

### Anticipated Start Date

25/05/2020

### Sources of Funding

NIL

### Conflict of Interest

NIL

### Ethical Approval

The UK National Research Ethics Service decision tool confirmed this study does not require ethical approval. It has been registered locally within our hospital trust Research and Development team.

### Sponsorship and Governance

An Integrated Research Application System (IRAS) form was completed (registration number 285260) and copies of the protocol submitted to Barking, Havering and Redbridge University NHST Trust (BHRUT) for sponsorship review and for Health Research Authority (HRA) approval. The protocol was subsequently submitted to clinicaltrials.gov (NCT number 133196) for registration.

### Participants/Study Population

All adult patients (>17 years) undergoing emergency (general) surgery at a single centre (Queens Hospital, Romford, UK) regardless of COVID-19 status will be included. Patients will be organised into those with:

- a) suspected or confirmed COVID-19 (diagnosed clinically, radiologically or with positive viral PCR); and
- b) those for whom COVID-19 was not suspected.

Diagnosis or suspicion of COVID-19 must be made between 7-days before and 30-days after date of surgery in accordance with the COVIDSurg study criteria.

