### Study Questions

- 1) Is NLR a predictor of negative outcomes in patients undergoing emergency general surgery?
- 2) Is NLR different in COVID positive versus COVID negative patients undergoing emergency general surgery?

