### Data Collection

Data will be collected using a data extraction template. This will be piloted on 5 included patients and refined as appropriate. Data will be collected from electronic sources including (but not limited to) BlueSpier, EPRO, Cyberlab and Medway. Data will include baseline patient characteristics, operation performed, COVID status and diagnostic method, NLR (pre-operative/day 0 (D0), D1, D2 and D3) and the aforementioned outcome measures. Data will be collected for 30-days following on from the date of surgery.

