### Data Synthesis

For dichotomous outcome measures Relative Risk (RR) will be calculated and significance testing completed using Chi-Squared or Fisher's exact test depending on sample sizes. For continuous variables standardised mean difference (SMD) will be calculated and unpaired, two-tailed student's t-tests used for significance testing.

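### Unadjusted comparisons in a cohort pooled over COVID-19 status and operation type cannot show that NLR predicts 30-day mortality beyond COVID-19 status, age or operation

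*Combined protocol and SAP*

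**What the plan says.** The Study Design section gives the design as "Observational study". Under Participants/Study Population, adults having emergency general surgery at one centre "regardless of COVID-19 status will be included", with no restriction by operation. The same section then forms two COVID-19 groups ("Patients will be organised into those with" introduces the definitions) and sets the timing: "Diagnosis or suspicion of COVID-19 must be made between 7-days before and 30-days after date of surgery".

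Study Questions asks, first, "Is NLR a predictor of negative outcomes in patients undergoing emergency general surgery" and, second, "Is NLR different in COVID positive versus COVID negative patients undergoing emergency general surgery". The primary outcome is death by 30 days.

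On what is recorded, Data Collection says: "Data will include baseline patient characteristics, operation performed, COVID status and diagnostic method". It adds NLR from day 0 to day 3, and the outcomes.

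Data Synthesis is the whole analysis plan. For binary outcomes, "Relative Risk (RR) will be calculated and significance testing completed using Chi-Squared or Fisher's exact test". For continuous variables it gives a standardised mean difference with an unpaired t-test. It names no covariate, stratified estimate, matching or regression model.

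**The concern.** Question 2 treats COVID-19 as something that may shift NLR. If it does, and if COVID-19 also raises 30-day mortality, then high-NLR patients will die more often partly because more of them have COVID-19. Age and the type of operation could act in the same way. The variables that would help to separate these explanations are at least partly recorded, but the plan gives them no role in Question 1.

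What is at stake is how the main result can be read. A pooled crude relative risk above 1 fits two accounts equally well. In one, NLR carries prognostic information of its own. In the other, NLR marks COVID-19, older age or a bigger operation, all of which the clinician already knows. A crude figure also depends on the mix of COVID-19 cases during the collection window, so it may not carry over to another period. Choosing an NLR cut-off or measurement day would not remove the problem.

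**Working it through.** **No planned figure to reproduce.** The documents give no sample size target, power, event rate, effect size, NLR cut-off or COVID-19 prevalence. Every input below is therefore an assumption, chosen to show a range.

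**One confounder (COVID-19).** Let
- p = share of the cohort with COVID-19
- h1, h0 = proportion with high NLR, with and without COVID-19
- m1, m0 = 30-day mortality, with and without COVID-19

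NLR is given no effect on death within either group, so the within-group relative risk is 1.00 by construction. Then

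- P(high) = p·h1 + (1−p)·h0
- mortality if high = [p·h1·m1 + (1−p)·h0·m0] / P(high)
- mortality if low = [p·(1−h1)·m1 + (1−p)·(1−h0)·m0] / [1 − P(high)]
- crude RR = mortality if high / mortality if low

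The grid was p = 10, 20, 30%; h1 = 60, 70, 80% with h0 = 40%; and (m1, m0) = (10%, 5%), (20%, 5%), (25%, 3%).

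| Case | p | h1 / h0 | m1 / m0 | Mortality if high | Mortality if low | Crude RR |
|---|---|---|---|---|---|---|
| Weakest | 10% | 60 / 40% | 10 / 5% | 0.024/0.42 = 5.71% | 0.031/0.58 = 5.34% | 1.07 |
| Middle | 20% | 70 / 40% | 20 / 5% | 0.044/0.46 = 9.57% | 0.036/0.54 = 6.67% | 1.43 |
| Strongest | 30% | 80 / 40% | 25 / 3% | 0.0684/0.52 = 13.15% | 0.0276/0.48 = 5.75% | 2.29 |

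The chance that the crude comparison reaches two-sided p < 0.05 (an assumed level) at assumed totals of 100, 200 and 400 patients is 8%, 12% and 19% in the middle case, and 24%, 43% and 71% in the strongest.

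**Two confounders (COVID-19 and older age).** Assume 20% have COVID-19 and 35% are older, independently. Base mortality is 2%, multiplied by 4 for each factor. P(high NLR) is 30%, plus 30 points for COVID-19 and 20 points for older age. Again NLR has no effect of its own.

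| COVID-19 / older | Share | P(high) | Mortality |
|---|---|---|---|
| no / no | 0.52 | 0.30 | 2% |
| no / yes | 0.28 | 0.50 | 8% |
| yes / no | 0.13 | 0.60 | 8% |
| yes / yes | 0.07 | 0.80 | 32% |

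- High NLR: 0.03848/0.43 = 8.9% mortality.
- Low NLR: 0.02712/0.57 = 4.8% mortality.
- Crude RR = 1.88, with a 14%, 23% or 39% chance of p < 0.05 at 100, 200 or 400 patients.

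Operation type was not quantified. That the cohort spans many operations is inferred from the unrestricted eligibility and from the operation being recorded.

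**Timing of COVID-19 status.** NLR is measured on days 0 to 3, but COVID-19 can be assigned up to day 30. The group label can therefore postdate the NLR value, so any adjusted analysis has to say which status it uses.

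**The case against.** The strongest reply is that Question 1 asks about prediction. It does not ask about an independent predictor or a cause, and a crude association properly answers whether NLR is related to outcome in this population. That stands. A reader might infer that the crude relative risk is invalid, or that any association found would be spurious. The documents support neither. They support only that the plan cannot show what NLR adds to COVID-19 status, age and operation.

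A reader might also infer that COVID-19 status is collected and then ignored. That is not so: the two groups are defined, and the t-test in Data Synthesis is the evident analysis for Question 2. The gap is confined to Question 1.

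The size is open to challenge too. Large crude relative risks need strong assumed links, and weaker inputs give a value close to 1.1. It would be wrong to read a doubling of risk as the expected artefact.

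Finally, deaths may be too few to support adjustment. The plan gives no expected number, so this is a real possibility. It limits how many covariates can be used, but it does not make the crude figure evidence of added value.

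**Conclusion.** The point holds in a limited form. As planned, the study can describe a marginal association between NLR and 30-day mortality, but it cannot support a statement that NLR predicts death beyond COVID-19 status, age or operation. That there is no adjusted or within-group estimate for Question 1 is plain from Data Synthesis.

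The size of the consequence is not known. Under the assumed inputs, COVID-19 alone moves a within-group relative risk of 1.00 to a crude value anywhere from about 1.07 to 2.29, and COVID-19 with age gives 1.88 in one scenario. The documents give no basis for choosing within that range. The study can run without the change, but it should be made because it is cheap and bears on the primary outcome.

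**What to change.** In Data Synthesis:

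1. Keep the crude relative risk for Question 1 and label it descriptive.
2. Report the Question 1 mortality result separately by COVID-19 group.
3. Base any claim of added predictive value on one pre-specified estimate adjusted for COVID-19 status, age and a simple operation category defined in advance. Penalised logistic regression is suitable. Report the odds ratio, or convert it to a standardised relative risk to match the plan's chosen measure.
4. If deaths are too few for that model, use a Mantel-Haenszel relative risk by COVID-19 status, and state that it does not adjust for age or operation.
5. Take COVID-19 known or suspected by the time of surgery as the main definition, so that a later event is not adjusted for. Use the day −7 to +30 definition as a sensitivity analysis, because some patients diagnosed soon after surgery may already have been infected when NLR was measured.

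In Data Collection, make sure the extraction template records age, the date of COVID-19 diagnosis or suspicion, and the operation category. None of the three is itemised now, so it should not be assumed that everything needed is already captured.

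The cost is a few sentences, a small extra analysis, possibly a small change to the template, and a wider interval if deaths are few.

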### Planned Study Period

Data will be collected on all patients meeting criteria undergoing emergency surgery on or after the date of UK lockdown due to COVID-19 (23th March 2020) until 22nd May 2020. If sample size is small then the end date for data collection will be extended.

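### Question 2 is worded as COVID positive versus negative, but the groups compare suspected-or-confirmed with not suspected, so its answer carries misclassification bias of unknown direction

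*Combined protocol and SAP*

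**What the plan says.** All references are to the combined protocol and SAP.

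- **Study Questions**, second item: "Is NLR different in COVID positive versus COVID negative patients undergoing emergency general surgery".
- **Participants/Study Population**, group (a): "suspected or confirmed COVID-19 (diagnosed clinically, radiologically or with positive viral PCR"). PCR is one of three alternative routes into the group.
- **Participants/Study Population**, group (b): "those for whom COVID-19 was not suspected". No negative test is needed to enter it.
- **Participants/Study Population**, timing: "Diagnosis or suspicion of COVID-19 must be made between 7-days before and 30-days after date of surgery", following the criteria of an external cohort study.
- **Data Collection**: the extracted items include "COVID status and diagnostic method" and "NLR (pre-operative/day 0 (D0), D1, D2 and D3").
- **Data Synthesis**: continuous variables are summarised by a standardised mean difference, with "unpaired, two-tailed student's t-tests used for significance testing". No analysis by diagnostic route is planned.

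No section equates positive and negative with groups (a) and (b). None says where a patient goes who was suspected and then tested PCR-negative.

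**The concern.** The question is about infection and the groups are about suspicion. Group (a) can contain uninfected patients who looked as if they had COVID-19, and group (b) can contain infected patients whom nobody suspected. A conclusion headed COVID positive versus negative would claim more than the comparison can show.

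Timing adds to this. A patient first suspected on day 20 belongs to group (a), although the NLR values analysed come from days 0 to 3. A post-operative complication could also raise the NLR and prompt the suspicion. The label is then not independent of the measurement.

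Question 2 is one of only two study questions. Without a planned split by diagnostic route, neither a null nor a positive answer can be read with confidence as a statement about infection.

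**Working it through.** **1. The plan's own figure.** There is none to reproduce. The plan gives no sample size, expected NLR difference, SD, or proportion infected in either group. Everything below is an illustration on stated assumptions.

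**2. Question and groups side by side.**

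| | Question 2 | Groups defined |
|---|---|---|
| First group | COVID positive | Clinical, radiological or PCR route; suspicion is enough |
| Second group | COVID negative | Not suspected; no test required |
| Suspected, then PCR-negative | Not addressed | Placement not stated |
| Analysis by diagnostic route | – | None planned, although the route is recorded |

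The mismatch follows from the text alone and needs no arithmetic.

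**3. What misclassification does to the mean difference.** Work in SD units and set the mean of typical uninfected patients to 0. Let

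- *d* = true infected-minus-uninfected difference (assumed 0.5);
- PPV = share of group (a) truly infected (assumed 0.5 to 0.9);
- NPV = share of group (b) truly uninfected (assumed 0.95);
- *s* = how far the NLR of uninfected patients in group (a) lies above that of other uninfected patients (assumed 0 to 1).

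Then

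- mean of (a) = PPV × *d* + (1 − PPV) × *s*
- mean of (b) = (1 − NPV) × *d*
- observed difference = mean of (a) − mean of (b)

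With *s* = 0 this reduces to *d* × (PPV + NPV − 1), the usual dilution formula.

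**4. Numbers at PPV 0.7, NPV 0.95, *d* = 0.5.**

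- *s* = 0: 0.7 × 0.5 + 0.3 × 0 − 0.05 × 0.5 = 0.350 − 0.025 = 0.325; ratio to truth 0.325/0.5 = **0.65**.
- *s* = 0.5: 0.350 + 0.150 − 0.025 = 0.475; ratio **0.95**.
- *s* = 0.75: 0.350 + 0.225 − 0.025 = 0.550; ratio **1.10**.
- *s* = 1.0: 0.350 + 0.300 − 0.025 = 0.625; ratio **1.25**.

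The bias changes sign where 0.325 + 0.3*s* = 0.5, that is *s* = 0.175/0.3 = 0.58 SD.

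**5. Sensitivity to the assumed PPV (NPV 0.95, *d* = 0.5): observed/true ratio.**

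| PPV | *s* = 0 | *s* = 0.5 | *s* = 0.75 | *s* = 1.0 |
|---|---|---|---|---|
| 0.9 | 0.85 | 0.95 | 1.00 | 1.05 |
| 0.7 | 0.65 | 0.95 | 1.10 | 1.25 |
| 0.5 | 0.45 | 0.95 | 1.20 | 1.45 |

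At PPV 0.9 the ratio stays between 0.85 and 1.05. At PPV 0.5 it runs from less than half the true difference to almost one and a half times it. The documents do not say which row or column applies.

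**The case against.** The grouping is explicit and disclosed. All three diagnostic routes are listed and the time window follows an external cohort's criteria. A reader could take positive and negative as shorthand for the only groups the protocol defines. Diagnostic method is recorded, so a split could be made later without new data. All of this is fair. It means the grouping need not be replaced and that nothing is irrecoverably lost. It does not supply the missing definition, and a split chosen after the results are seen is weaker than one stated beforehand.

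Two stronger readings are tempting, and the documents support neither.

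- *A reader might infer that the NLR difference is necessarily diluted.* That holds only if misclassification is unrelated to NLR. Suspicion can depend on how ill the patient is, and the difference may then be unchanged or inflated.
- *A reader might infer that a PCR-only comparison would have more power.* This depends entirely on assumed group sizes. Take a two-sided 5% test, *d* = 0.5 and 2–10% infected in group (b). Then 15 confirmed versus 120 not suspected gives 37–43% power, and 10 confirmed versus 120 gives 27–32%. The full grouping at 30 versus 120 gives 31–38% if 70% of group (a) are infected and 40–48% if 80% are. The ordering can go either way, so power is no argument for the change.

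It is also true that a PCR split is not a clean remedy. PCR testing may itself have been prompted by severity, and unsuspected patients are not proven negative. The reporting has to say so.

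**Conclusion.** The point holds as a mismatch between question and groups, with bias of unknown direction. The mismatch is shown by the Study Questions and Participants/Study Population sections alone. The size is illustrative: 0.65 to 1.25 times the true difference at PPV 0.7, NPV 0.95, a true difference of 0.5 SD, and a shift of 0 to 1 SD in uninfected suspected patients. None of these inputs comes from the plan.

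The consequence is confined to Question 2. Question 1 and the primary outcome, 30-day mortality, do not use this grouping as written. This is a cheap improvement to the plan and does not undermine the study.

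**What to change.** 1. Keep groups (a) and (b) as the main grouping, and reword Question 2 to 'suspected or confirmed versus not suspected'.
2. State which group a suspected but PCR-negative patient falls in.
3. Pre-specify a sensitivity analysis of Question 2, using the recorded diagnostic method: PCR-confirmed patients versus group (b), and versus PCR-negative patients where tests exist.
4. Tabulate NLR for three categories: PCR-confirmed, suspected only, and not suspected.
5. Limit COVID positive wording to the PCR-confirmed result. Note beside it that PCR testing may have been selected on severity and that unsuspected patients are not proven negative.

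**Cost.** One reworded question, one placement rule and one extra table. Diagnostic method is already extracted; the PCR-negative comparison can be made only where results exist. The PCR-confirmed group will be smaller than group (a), so its interval will be wider. It should be read beside the main comparison and not in place of it.

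### On its natural reading, Question 2 pools COVID-19 known at NLR sampling with COVID-19 first suspected up to day 30; a pre-specified split by timing would separate them at little cost

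*Combined protocol and SAP*

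**What the plan says.** All references are to the Combined protocol and SAP.

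- **Participants/Study Population** forms two groups. Group a) has suspected or confirmed COVID-19, and group b) is "those for whom COVID-19 was not suspected". The timing rule is "Diagnosis or suspicion of COVID-19 must be made between 7-days before and 30-days after date of surgery", attributed to the COVIDSurg criteria.
- **Study Questions**, Question 2, asks: "Is NLR different in COVID positive versus COVID negative patients undergoing emergency general surgery"? It does not say how positive and negative are defined.
- **Data Collection** states: "Data will include baseline patient characteristics, operation performed, COVID status and diagnostic method, NLR (pre-operative/day 0 (D0), D1, D2 and D3"), together with the outcome measures. The date of diagnosis or suspicion is not named. On the template it says "This will be piloted on 5 included patients and refined as appropriate", and on follow-up "Data will be collected for 30-days following on from the date of surgery".
- **Data Synthesis** gives the whole analysis for NLR as a continuous variable: "For continuous variables standardised mean difference (SMD) will be calculated", with a two-sided t-test for independent groups.

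No section plans a subgroup, restriction or sensitivity analysis by timing of COVID-19 diagnosis.

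**The concern.** The grouping variable can be settled up to 30 days after surgery, but the measurement being compared ends on day 3. Group a) can therefore contain two kinds of patient: those whose COVID-19 was known or suspected when the blood was taken, and those first diagnosed or suspected afterwards, some of whom may not have been infected at sampling. Membership of group b) is likewise final only when the window closes.

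What is at stake is what Question 2 can conclude. The pooled SMD describes early NLR in patients with and without COVID-19 at any time in the peri-operative window. It does not by itself describe NLR in patients who had COVID-19 at the time of surgery. A reader is likely to take it that way, and the plan offers no result that would tell the two apart.

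**Working it through.** The plan states no SMD, sample size, group share or distribution of diagnosis dates, so it has no figure to reproduce. The structural point needs none. The numbers below only show how far the pooled result could move.

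**Sections side by side.** COVID-19 window: day −7 to day +30. NLR samples: days 0, 1, 2 and 3. Any first diagnosis or suspicion from day 4 to day 30 follows every NLR sample, and any from day 1 onwards follows the day 0 sample. The analysis treats all these patients as one group.

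**Inputs (all assumed).**
- d = 0.50: SMD between patients known or suspected by the sample and patients never suspected.
- s: share of group a) first diagnosed or suspected after the sample.
- f: fraction of d carried by those later patients. f = 0 means that they resemble the comparator at sampling, f = 1 that they carry the full difference, and f = 1.5 that a high early NLR tends to precede later suspicion.

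**Formula.** Pooled SMD = d × [(1 − s) + s × f].

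| s | f = 0 | f = 0.5 | f = 1 | f = 1.5 |
|---|---|---|---|---|
| 0.25 | 0.375 | 0.4375 | 0.50 | 0.5625 |
| 0.50 | 0.25 | 0.375 | 0.50 | 0.625 |

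With few later cases the effect is small: s = 0.05 and f = 0 give 0.50 × 0.95 = 0.475. The slight increase in variance from mixing is ignored. If group a) is 20% of patients, it would change 0.375 to about 0.373 and 0.25 to about 0.248.

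**Read backwards.** With s = 0.50, an observed pooled SMD of 0.25 fits d = 0.25 / (0.5 + 0.5 × 0) = 0.50, and equally d = 0.25 / (0.5 + 0.5 × 1.5) = 0.20. The pooled figure cannot distinguish these. A separate SMD for patients known by surgery estimates their difference directly.

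**Precision of a split.** Assume 200 patients, 40 in group a) and 160 never suspected. The approximate 95% CI half-width for an SMD is 1.96 × √(1/n₁ + 1/n₂):
- whole of group a), 40 v 160: 1.96 × √(0.025 + 0.00625) = 0.35
- 30 v 160: 1.96 × √(0.0333 + 0.00625) = 0.39
- 20 v 160: 1.96 × √(0.05 + 0.00625) = 0.46
- 10 v 160: 1.96 × √(0.10 + 0.00625) = 0.64

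**The case against.** **The window is declared and sourced.** This stands. A window taken from COVIDSurg is reasonable for describing peri-operative COVID-19, and whether early NLR differs between patients with and without it is a valid descriptive question. A reader might infer that the window is an error, or that Question 2 cannot be answered. The documents support neither. They only leave unsaid which patients the answer describes.

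**The link to the groups is inferred.** This also stands. Question 2 speaks of positive and negative, whereas the Participants section speaks of suspected or confirmed and of not suspected. No other definition is given, so identifying the two is natural, but it should be written down.

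**Size and direction are unknown.** Correct. It is tempting to note that 27 of the 38 window days (71%) fall after day 3 and to conclude that most cases are late. Calendar days are not patients, and the documents give no share of late diagnoses. Nor do they support a claim that the bias must be towards no difference.

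**The date must be recorded anyway.** Largely right. The window cannot be applied without it, and the list of data items is not presented as complete. Naming the date is a clarification. But having the date does not help if no analysis uses it.

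**The declared grouping should be replaced.** A reader might infer that status should be redefined at each sample, with everyone not yet suspected as comparator. That is a trade-off and not a clear gain. With the 200 patients above, SMD divided by its standard error is lower under such regrouping in 6 of the 8 combinations of s and f. At s = 0.50 it is 2.12, 2.00, 1.89 and 1.77 for f = 0, 0.5, 1 and 1.5, against 1.41, 2.12, 2.83 and 3.54 as declared. At f = 1.5 part of the declared grouping's advantage is inflation. Patients would also change groups between day 0 and day 3, so the course of NLR would no longer be compared in fixed groups.

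**Conclusion.** The point holds as a cheap improvement to Question 2. On the natural reading of the groups, the planned comparison mixes COVID-19 known or suspected at sampling with COVID-19 first suspected later, and nothing planned separates them. This rests on the sections themselves and on that reading.

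The consequence is less certain. Later cases may dilute the NLR difference, leave it unchanged or widen it. The range of 0.25 to 0.63 around an assumed 0.50 depends wholly on assumed shares of 25% or 50% later cases and on what those cases carry. With few later cases the pooled result would hardly move. Question 1 in all patients is not affected.

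**What to change.** 1. In Study Questions or Data Synthesis, state that Question 2 uses groups a) and b) of the Participants section, and keep the declared −7 to +30 day grouping.
2. Beside it, pre-specify a split of group a) into three fixed groups by date of first diagnosis or suspicion: on or before the day of surgery, days 1 to 3, and after day 3.
3. For each group, report NLR at each sample and the SMD with 95% CI against patients never suspected. Base any statement about NLR in patients with COVID-19 at the time of surgery on the first group.
4. Label the later groups and the never-suspected comparator as defined by information that arose after sampling.
5. Name the date of first diagnosis or suspicion as a data item.

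**Cost.** One date field that the window already requires, in a template still to be piloted and refined, and a modest amount of extra analysis. No follow-up is needed beyond the planned 30 days. The subgroups are smaller: if the assumed 40 patients split 20, 10 and 10, the half-widths are 0.46, 0.64 and 0.64, against 0.35 for the whole group. The protocol already provides that "If sample size is small then the end date for data collection will be extended", though it gives no target number. Patients who were infected but never diagnosed or suspected cannot be identified under either grouping, and this should be stated as a limitation.
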